**9.10 Expected vs. Unexpected Events**

*Expected events* - are those described within the Section 9.10 of the protocol, the study specific consent form, package insert (if applicable), and/or the investigator brochure, (if an investigator brochure is not required, otherwise described in the general investigational plan).

*Unexpected adverse events* or suspected adverse reactions are those not listed in Section 10.2 of the protocol, the study specific consent form, package insert (if applicable), or in the investigator brochure (or are not listed at the specificity or severity that has been observed); if an investigator brochure is not required or

available, is not consistent with the risk information described in the general investigational plan.

*Unexpected* also refers to adverse events or suspected adverse reactions that are mentioned in the investigator brochure as occurring with a class of drugs but have not been observed with the drug under investigation.

An investigational agent/intervention might exacerbate the expected AEs associated with a commercial agent. Therefore, if an expected AE (for the commercial agent) occurs with a higher degree of severity or specificity, expedited reporting is required.

### 9.11 Attribution to Agent(s) or Procedure

When assessing whether an adverse event (AE) is related to a medical agent(s) medical or procedure, the following attribution categories are utilized:

Definite - The AE is *clearly related* to the agent(s)/procedure.

Probable - The AE is *likely related* to the agent(s)/procedure.

Possible - The AE *may be related* to the agent(s)/procedure.

Unlikely - The AE is *doubtfully related* to the agent(s)/procedure.

Unrelated - The AE is *clearly NOT related* to the agent(s)/procedure.

CTCAE  System Organ Class (SOC)	Adverse event/ Symptoms	CTCAE Grade at which the event will not be reported in an expedited manner 
Vascular Disorders	Hot flashes	≤Grade 3
Musculoskeletal and Connective Tissue Disorders	Generalized muscle weakness	≤Grade 3
Gastrointestinal Disorders	Nausea	≤Grade 3
Nervous System Disorders	Paresthesia	≤Grade 3

 Report any CTCAEs on <https://prevention.cancer.gov/clinical-trials/clinical-trials-management/cp-ctnet-instructions-forms> Additional instructions: The research coordinator will work with Site PI and complete IRB reporting to determine if FDA submission is needed.

**Grades** from aforementioned CTCAE site:

Grade refers to the severity of the AE. The CTCAE displays Grades 1 through 5 with unique clinical descriptions of severity for each AE based on this general guideline:

**Grade 1** Mild; asymptomatic or mild symptoms; clinical or diagnostic observations only; intervention not indicated.

**Grade 2** Moderate; minimal, local or noninvasive intervention indicated; limiting age-appropriate instrumental ADL\*.

**Grade 3** Severe or medically significant but not immediately life-threatening; hospitalization or prolongation of hospitalization indicated; disabling; limiting self-care ADL\*\*.

**Grade 4** Life-threatening consequences; urgent intervention indicated.

**Grade 5** Death related to AE.

These exceptions only apply if the adverse event does not result in hospitalization. If the adverse event results in hospitalization, then the standard expedited adverse events reporting requirements must be followed.

## 10.0 Other Required Reporting

### 10.1 Unanticipated Problems Involving Risks to Subjects or Others (UPIRTSOS)

Unanticipated Problems Involving Risks to Subjects or Others (UPIRTSOS) in general include any incident, experience, or outcome that meets **all** of the following criteria:

- 10.1.1 Unexpected (in terms of nature, severity, or frequency) given (a) the research procedures that are described in the protocol-related documents, such as the IRB-approved research protocol and informed consent document; and (b) the characteristics of the subject population being studied;
- 10.1.2 Related or possibly related to participation in the research (in this guidance document, possibly related means there is a reasonable possibility that the incident, experience, or outcome may have been caused by the procedures involved in the research); and
- 10.1.3 Suggests that the research places subjects or others at a greater risk of harm (including physical, psychological, economic, or social harm) than was previously known or recognized.

Some unanticipated problems involve social or economic harm instead of the physical or psychological harm associated with adverse events. In other cases, unanticipated problems place subjects or others at increased *risk* of harm, but no harm occurs.

### 10.2 Serious Adverse Event (SAE) Monitoring and Reporting

The site principal investigator is responsible for reporting any/all serious adverse events to the sponsor as described within the protocol, regardless of attribution to study agent or treatment procedure.

The site principal investigator is responsible for notifying FDA, Mayo Clinic Department of Surgery Data Safety Monitoring Board, and all participating investigators in a written safety report of any of the following:

- Any suspected adverse reaction that is both serious and unexpected.
- Any findings from epidemiological studies, pooled analysis of multiple studies, or clinical studies, whether or not conducted under an IND and whether or not conducted by the sponsor [name]., that suggest a significant risk in humans exposed to the drug.
- Any clinically important increase in the rate of a serious suspected adverse reaction over the rate stated in the protocol.
- Grade 4 AEs regardless of attribution to the study treatment or procedure.
- Grade 5 AEs (Deaths)
- Any death within 30 days of the patient's last study treatment or procedure regardless of attribution to the study treatment or procedure.
- Any death more than 30 days after the patient's last study treatment or procedure that is felt to be at least possibly treatment related must also be submitted as a Grade 5 AE, with a CTCAE type and attribution assigned.

## SAE Reporting Summary

WHO	SAE	WHAT FORM	WHERE TO SEND
All sites	Pregnancy Reporting	https://prevention.cancer.gov/clinical-trials/clinical-trials-management/cp-ctnet-instructions-forms	[contact]
		MedWatch 3500A: http://www.fda.gov/downloads/AboutFDA/ReportsManualsForms/Forms/UCM048334.pdf	The Mayo Clinic Office of Research and Regulatory Support will assist Mayo Clinic Rochester in filing the MedWatch 3500A form to the FDA. Please refer to section 10.3 for reporting timelines. Mayo Clinic Rochester will report the SAE to the following: DCP Regulatory Contractor, CCS Associates: [contact]
All sites	FDA Reporting	MedWatch 3500A: http://www.fda.gov/downloads/AboutFDA/ReportsManualsForms/Forms/UCM048334.pdf	[contact]
All sites	SAEs	Mayo Clinic Department of Surgery Data and Safety Monitoring Board (DSMB)	Mayo Clinic Rochester will contact DSMB within 24 hours of notification of SAE

Mayo Clinic Rochester study team will contact the Mayo Clinic Department of Surgery (DOS) Data and Safety Monitoring Board (DSMB) within 24 hours of notification of SAE. The team will also report as indicated in section 10.2 SAE Reporting Summary.

Report the following SAE information when contacting the Mayo Clinic Department of Surgery (DOS) Data and Safety Monitoring Board (DSMB):

- Date and time of the SAE
- Date and time of the SAE report
- SAE description and attribution to drug
- Reporter name, email, and telephone number
- Affiliation/Institution where SAE occurred
- DCP and IRB protocol number
- Title of protocol

**10.2.1** An initial assessment of the SAE will be made by the DSMB. The study team will submit to the Institutional Review Board who will determine which SAEs require FDA submission as IND safety reports as noted in section 10.2.

**10.2.2** Follow-up of SAE

Mayo Clinic, Northwestern University and MD Anderson Cancer Center at Cooper will send requested follow-up reports to DCP as soon as possible. This information should be entered on the DCP SAE Report Form.

BHIR Besins Pharmacovigilance will not have any monitoring or reporting requirements. Besins will receive reports at the time of the annual Continuing Review.

**10.3 Expedited Reporting Requirements for IND Agents**

Late Phase 2 and Phase 3 Studies: Expedited Reporting Requirements for

Adverse Events that Occur on Studies under an IND/IDE within 30 days of the Last Administration of the Investigational Agent/Intervention.

**FDA REPORTING REQUIREMENTS FOR SERIOUS ADVERSE EVENTS (21 CFR Part 312)**

**NOTE:** Investigators **MUST** immediately report to the sponsor (NCI) **ANY** Serious Adverse Events, whether or not they are considered related to the investigational agent(s)/intervention (21 CFR 312.64)

An adverse event is considered serious if it results in **ANY** of the following outcomes:

- 1) Death
- 2) A life-threatening adverse event
- 3) An adverse event that results in inpatient hospitalization or prolongation of existing hospitalization for  $\geq 24$  hours
- 4) A persistent or significant incapacity or substantial disruption of the ability to conduct normal life functions
- 5) A congenital anomaly/birth defect.
- 6) Important Medical Events (IME) that may not result in death, be life threatening, or require hospitalization may be considered serious when, based upon medical judgment, they may jeopardize the patient or subject and may require medical or surgical intervention to prevent one of the outcomes listed in this definition. (FDA, 21 CFR 312.32; ICH E2A and ICH E6).

**ALL SERIOUS** adverse events that meet the above criteria **MUST** be immediately reported to the NCI via AdEERS within the timeframes detailed in the table below.

Hospitalization	Grade 1 Timeframes	Grade 2 Timeframes	Grade 3 Timeframes	Grade 4 & 5 Timeframes
Resulting in Hospitalization $\geq 24$ hrs.		10 Calendar Days		24-Hour 5 Calendar Days
Not resulting in Hospitalization $\geq 24$ hrs.	Not required		10 Calendar Days	

**NOTE:** Protocol-specific exceptions to expedited reporting of serious adverse events are found in the Specific Protocol Exceptions to Expedited Reporting (SPEER) portion of the CAEPR

**Expedited AE reporting timelines are defined as:**

- o “24-Hour; 5 Calendar Days” - The AE must initially be reported via AdEERS within 24 hours of learning of the AE, followed by a complete expedited report within 5 calendar days of the initial 24-hour report.
- o “10 Calendar Days” - A complete expedited report on the AE must be submitted within 10 calendar days of learning of the AE.

Serious adverse events that occur more than 30 days after the last administration of investigational agent/intervention and have an attribution of possible, probable, or definite require reporting as follows:

**Expedited 24-hour notification followed by complete report within 5 calendar days for:**

- All Grade 4, and Grade 5 AEs

**Expedited 10 calendar day reports for:**

- Grade 2 adverse events resulting in hospitalization or prolongation of hospitalization
- Grade 3 adverse events

 For studies using PET or SPECT IND agents, the AE reporting period is limited to 10 radioactive half-lives, rounded UP to the nearest whole day, after the agent/intervention was last administered. Footnote “1” above applies after this reporting period.

Effective Date: May 5, 2011

## 10.4 Protocol Deviations

Minor protocol deviations must be documented and reported at the time of continuing review. Notifying the IRB through a reportable Event submission is required if a deviation that imposes a suspected increase in the risk of harm to participants or adversely affects the integrity of the data.

Study staff will refer to the protocol and study specific SOPs, institutional and departmental policies. All associated source documents will be collected, including all pertinent outside medical information, which will be reviewed and assessed by the PI or Co-investigator. The PI will determine whether event meets UPIRTSO or significant new information criteria and/or protocol violation/deviation definition.

Events will be reported per the Investigator's direction in alignment with the institutional policies to:

- Mayo IRB
- Data Safety Monitoring Board (DSMB)
- Food and Drug administration (FDA)- if Mayo sponsor/investigator holds the Investigational New Drug (IND) or Investigational Device Exemption, (IDE) contact Office of Research Regulatory Support (ORRS)

(See Section 10.0 Other Required Reporting)

Event will be documented in the Deviation Log at Mayo Clinic and all associated documentation will be retained. Northwestern University and MD Anderson Cancer Center at Cooper will follow their institutional policy for documentation.

## **11.0 Statistical Considerations**

The primary hypothesis is that the reduction in Ki67 will not be inferior to that seen with oral tamoxifen. A sample size of 36 per treatment arm (36 receiving oral tamoxifen and 36 receiving 4OHT gel, with 18 placebo controls) will provide >80% power at  $\alpha=0.05$  to test this hypothesis. Volume density and MBI will be compared across study arms from pre-to post-treatment. Risk predictors identified from Nanostring-based mRNA expression assay (conducted under IRB 75-87) and biomarkers of tamoxifen response (conducted under IRB 15-000279) will also be tested.

*Randomization and intervention.* To achieve the planned sample size of N=90 women, we will over-accrue by ~15% to allow for cancellation, ineligibility, non-evaluable samples, or major treatment deviations and thus plan to enroll a total of N=104 at two study sites (42 at Mayo-Rochester, 42 at Northwestern University, 20 at MD Anderson Cancer Center at Cooper). Patients will be randomized 2:2:1 to oral Tam (10 mg/day), 4-OHT gel (4 mg/each breast/day), or placebo controls for four weeks. Estimated numbers of randomized subjects to each arm will be: 42 to oral Tam, 42 to 4OHT gel, and 21 double placebo, in order to arrive at final sample size of 36, 36, and 18. Treatment randomization will be stratified with respect to menopausal status (pre- vs. postmenopausal), diagnosis (ADH vs ALH/LCIS vs increased BC risk based on risk model calculations), and study site. Oral and gel placebos will be used to create a double-blinded study. After four weeks, blood draw, physical exam, BCPT symptom survey, digital mammogram (and MBI in Mayo subjects) will be repeated. A second breast tissue sample will be obtained from the same quadrant, either as a core biopsy or as tissue adjacent to the surgical excision site.

*Feasibility.* At Mayo Clinic in Rochester, MN, we see an average of 55 patients per year with ADH or ALH who would be eligible for this study. At Mayo Clinic, Drs. [name], [name], and [name] have successfully led accrual of over 500 women to prospective studies in the last six years, therefore successful accrual of women to this prospective study is feasible. At Northwestern University, there is a similar volume of women with diagnoses of ADH or ALH, and they have accrued ~400 women over five years to various studies requiring some form of intervention (either medication or biopsy). Accrual plan is for 42 subjects at Mayo Clinic, 42 at Northwestern University and 20 subjects at MD Anderson Cancer Center at Cooper. With an anticipated timeframe of 48 months to complete accrual, this averages to 1-2 patients per month per site. This study should be acceptable to patients as the duration of intervention is short and therefore short-term

toxicity is expected to be limited to only temporary vasomotor symptoms.

*Translational studies.* The primary endpoint will be change in Ki67 in background normal breast lobules (% cells positive by Aperio quantitation). Additional endpoints will include changes in volumetric density (% and dense volume) measured using VolparaTM both at baseline and after four weeks of treatment. In addition, promising genes from discovery work in Aim 2 will be evaluated using NanoString.

Changes in background parenchymal uptake (BPU) on MBI will also be employed as an exploratory endpoint. Blood samples and residual breast tissues collected pre/post Tam will be stored for future correlative studies.

*Endpoints.* The primary endpoint is change in Ki67 level pre/post treatment. The primary analysis for the primary endpoint will include all eligible patients who began study drug intervention and have available tissue measures of Ki67 levels at both timepoints (pre- and post-treatment).

A sensitivity analysis for the primary endpoint will also be performed. This sensitivity analysis will include eligible patients who have available tissue measures of Ki67 levels at both timepoints and were compliant with study treatment. Patients will be classified as non-compliant with the study treatment (and thus excluded from the sensitivity analysis) using criteria outlined above (patients who have less than 80% compliance with daily drug use or have missed more than 3 doses in the final 14 days).

As for the primary endpoint, primary analyses for secondary endpoints will include all eligible patients who began study drug and have available endpoint measurements at both timepoints; sensitivity analyses for each secondary endpoint will exclude non-compliant patients (as defined above). For analyses of adverse events, all patients who started the study treatment will be included, regardless of treatment compliance or availability of endpoint measurements at both timepoints.

*Statistical analysis.* The primary hypothesis is that the reduction seen with 4-OHT gel will be *not inferior* to that seen with oral tamoxifen. We also hypothesize that oral tamoxifen and 4-OHT gel will each be superior to placebo with respect to the percent change in Ki67 in background normal lobules between baseline and four weeks. Analyses will assess if significant changes in Ki67 are observed after four weeks of treatment by paired t-tests/Wilcoxon signed rank tests, stratified by treatment group. We will assess the non-inferiority of 4-OHT gel compared to oral tamoxifen by estimating a 95% confidence interval for the mean *difference* in percent change between the two agents after four weeks of treatment; if the lower limit of the confidence interval is less than the non-inferiority margin (described below), we will conclude that 4-OHT gel is non-inferior to oral tamoxifen. As exploratory analyses, we will assess pairwise differences between samples on active treatment (oral tamoxifen or 4-OHT gel, separately and combined) vs. placebo using two-sample t-tests/Wilcoxon rank sum tests. Similarly, we will assess changes from baseline in the expression of the candidate genes identified in Aim 2 (absolute log2 fold-change > 2 and/or q-value < 0.05). Volumetric density changes from baseline within treatment group will be assessed continuously, and evaluated using paired t-tests on the log-transformed density or Wilcoxon signed-rank tests; pairwise differences between treatment groups will be assessed with two-sample t-tests/Wilcoxon rank sum tests. BPU on MBI is measured as a four category ordinal scale; we will compare pre-to-post changes within group using Wilcoxon signed rank tests and will compare the percent of subjects decreasing BPU category by one or more level between groups using chi-square tests. We will assess the correlation between changes in volumetric density and changes in BPU, using Spearman correlation. Symptoms from the BCPT survey are measured on a five-level ordinal scale. We will compare differences in pre- to post-treatment symptom severity changes across

treatment arms using Wilcoxon rank sum tests.

**Sample size/power.** Prior studies suggest that oral tamoxifen will lead to a 50% mean relative reduction in Ki67 in normal lobules at four weeks compared to baseline.[19-21, 43] We assume that the standard deviation for the percent change in Ki67 is 30 percentage points, estimated based on a plausible range from published literature.[19-21, 43]] A sample size of 36 per active treatment arm will provide >80% power at  $\alpha=0.05$  to test the hypothesis that 4-OHT gel is not inferior to oral tamoxifen with a non-inferiority margin of 20 percentage points (e.g., if oral tamoxifen results in a 50% mean reduction of Ki67, 4-OHT gel will be considered non-inferior if we can conclude that 4-OHT gel results in a mean reduction of Ki67 of at least 30%). Further 18 subjects enrolled in a placebo arm will provide >90% power to detect a mean difference of 50% reduction for either treatment arm versus an assumed mean difference of 0% for placebo assuming a two-sided, two-sample t-test with  $\alpha=0.05$ . Therefore n=90 subjects are required, but the study will over-accrue by 15% (n=104 patients) to account for cancellation, ineligibility, non-evaluable samples, or major treatment deviations.

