## **6.0 Stratification Factors**

- Study site
- Diagnosis (ADH vs ALH/LCIS vs increased risk without AH or LCIS)
- Menopausal status (pre- vs. postmenopausal)

For the purposes of this trial, post-menopausal is defined as:

- A history of at least 12 months without spontaneous menstrual bleeding, or
- A prior documented hysterectomy and bilateral salpingo-oophorectomy, or
- A prior hysterectomy without oophorectomy or in whom the status of the ovaries is unknown, with a documented FSH level > or equal to 40, demonstrating confirmatory elevation in the postmenopausal range.

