## **6.1 Randomization Procedures**

**6.1.1** After the patient has completed the informed consent process, confirmed eligibility and the values of the stratification factors are recorded in Medidata RAVE, the patient will be assigned a research ID, and will be randomly assigned to one of the treatment groups.

Randomization will be performed using dynamic allocation, implemented within the Medidata RAVE system. The Medidata RAVE system will randomize the patient after the study coordinators have recorded the stratification factors as part of the blinded data input. Pharmacy will be notified of the randomization via email to a pharmacy email account prompting the pharmacist to log in and view the unblinded treatment assignment.

Randomization groups:

- Tamoxifen tablet, placebo gel
- 4-OHT gel, placebo tablet
- Control (placebo tablet, placebo gel)

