**Table 1. Sample size and power considerations for primary endpoint, non-inferiority in Ki67 change between gel and oral**

	Sample size & power assuming 15% attrition	Sample size & power assuming 10% attrition	Sample size & power assuming 5% attrition	Sample size & power assuming no attrition
Use entire sample,	36 per group (Power: 80%)	37 per group (Power 81%)	39 per group (Power 83%)	41 per group (Power: 85%)

including subjects with either 4 mg/day or 8 mg/day 4OHT gel				
Subgroup analysis including only those with 8 mg/day dose	36 oral Tam group, 31 in 8 mg/day 4OHT gel group (Power 76%)	37 oral Tam group, 32 in 8 mg/day 4OHT gel group (Power 78%)	39 oral Tam group, 34 in 8 mg/day 4OHT gel group (Power 80%)	41 oral Tam group, 36 in 8 mg/day 4OHT gel group (Power 82%)

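### The primary gel–tamoxifen interval uses none of the three factors that balance the randomisation; adjusting for them costs almost nothing and could tighten it

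*Combined protocol and SAP*

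**What the plan says.** Section 6.0 lists three stratification factors: study site, diagnosis (three levels) and menopausal status (two levels). Section 11.0 repeats them: "Treatment randomization will be stratified with respect to menopausal status (pre- vs. postmenopausal), diagnosis" and site. Section 6.1 gives the mechanism: "Randomization will be performed using dynamic allocation", run in Medidata RAVE once the factor values have been recorded.

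The primary comparison is in section 11.0 under the statistical analysis heading. It is a 95% confidence interval for the mean difference "in percent change between the two agents after four weeks of treatment". No model, covariate or stratified estimator is named. The word stratified occurs once in that analysis text, for the within-arm tests of change: "by paired t-tests/Wilcoxon signed rank tests, stratified by treatment group". The analysis sets, the sensitivity analyses and the power section do not use the factors either.

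The sample size rests on an overall spread: "We assume that the standard deviation for the percent change in Ki67 is 30 percentage points". With a 20-point margin, Table 1 gives 80% power at 36 women per active arm. For the subgroup on the 8 mg/day gel it gives 76% to 82%, depending on attrition.

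**The concern.** Balancing the arms on a prognostic factor removes that factor's contribution to chance differences between arms, so the true variance of the estimated difference falls. An unadjusted standard error does not reflect this, because it still contains the variation between factor levels. The interval is then too wide: coverage exceeds 95%, the one-sided error falls below 2.5%, and power that the design has already paid for is not used.

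The stake is precision in a comparison planned at about 80% power. There is also a pre-specification point. Because section 11.0 names no estimator, the choice between an adjusted and an unadjusted interval stays open until the data are seen.

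**Working it through.** **Inputs from section 11.0.** SD 30 points; margin 20 points; true difference 0; two-sided 95% interval, so 2.5% one-sided; 36 evaluable per active arm after 15% attrition.

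**Step 1: reproduce Table 1 without adjustment.** Power = P(T > t₀.₉₇₅), where T is noncentral t with n₁+n₂−2 df and noncentrality 20 / (30·√(1/n₁+1/n₂)). At 36/36 the standard error is 30·√(2/36) = 7.07, the noncentrality is 2.83, the interval half-width is 14.1 and power is 79.7%.

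| Evaluable n (tamoxifen/gel) | Computed | Table 1 |
|---|---|---|
| 36/36 | 79.7% | 80% |
| 37/37 | 80.8% | 81% |
| 39/39 | 82.8% | 83% |
| 41/41 | 84.7% | 85% |
| 36/31 | 76.4% | 76% |
| 37/32 | 77.7% | 78% |
| 39/34 | 80.0% | 80% |
| 41/36 | 82.2% | 82% |

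All eight agree after rounding. A one-sided 5% test would give 87.6% at 36/36 and does not fit. The stated power is therefore that of an unadjusted comparison.

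**Step 2: adjusted analysis under perfect balance.** Residual SD = 30·√(1−R²). The factors use 1+2+2 = 5 df, leaving 72−2−5 = 65. R² is not in the documents; 0 to 0.3 is an assumption.

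| R² | Residual SD | Half-width | Power at 36/36 | Power at 36/31 | Unadjusted one-sided error, 1−Φ(1.96/√(1−R²)) |
|---|---|---|---|---|---|
| 0 | 30.0 | 14.1 | 79.6% | 76.3% | 2.5% |
| 0.05 | 29.2 | 13.8 | 81.6% | 78.4% | 2.2% |
| 0.1 | 28.5 | 13.4 | 83.6% | 80.6% | 1.9% |
| 0.2 | 26.8 | 12.6 | 87.6% | 84.9% | 1.4% |
| 0.3 | 25.1 | 11.8 | 91.5% | 89.2% | 1.0% |

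**Step 3: simulation with imperfect balance and attrition.** From the plan: 104 women, sites 42/42/20, allocation 2:2:1, total SD 30. Assumed: Pocock–Simon minimisation with probability 0.8 for the best arm, 50% postmenopausal, diagnosis mix 40/30/30, 14% random attrition (mean 35.7 analysed per active arm), R² split equally over the factors. There were 20,000 runs per R²; Monte Carlo SE is about 0.3 point for power and 0.1 for error.

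| R² | Power, unadjusted | Power, adjusted | Change (points) | One-sided error, unadjusted | Mean CI width, adjusted |
|---|---|---|---|---|---|
| 0 | 78.7% | 78.0% | −0.7 | 2.4% | 28.6 |
| 0.05 | 79.8% | 80.4% | +0.6 | 2.4% | 27.8 |
| 0.1 | 80.1% | 82.7% | +2.6 | 2.1% | 27.1 |
| 0.2 | 80.8% | 86.6% | +5.8 | 1.7% | 25.5 |
| 0.3 | 81.9% | 90.8% | +8.9 | 1.2% | 23.9 |

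The unadjusted mean width is 28.3 to 28.4 throughout; the adjusted one-sided error is 2.5% to 2.7%.

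**Step 4: sensitivity to the assumptions.** A different minimisation scheme gives power changes of −0.8, +0.9, +2.2, +5.9 and +8.5 points. With all of R² on menopausal status, power is 79.9% unadjusted against 82.2% adjusted at R² = 0.1, and 81.3% against 87.0% at 0.2.

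**Step 5: is balancing the cause?** A separate simulation used 5,000 trials of 90 women, biased-coin probability 0.85 and half of R² on menopausal status. At R² = 0, 0.1, 0.2 and 0.3, coverage of the unadjusted interval under minimisation is 95.2%, 96.1%, 97.4% and 97.6%. Under simple randomisation it stays near 95% (94.7% to 95.3%). The conservatism therefore comes from balancing on the factors and then ignoring them.

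**The case against.** The strongest reply is that nothing here is wrong. An unadjusted interval after balanced allocation is valid and conservative, and the plan's power calculation matches it. This stands, and it limits the point to a suggested improvement.

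The benefit also rests on an R² that the documents do not give. Two of the four studies cited for the planning figures have premenopausal women in their titles, and section 2.0 reports a DCIS trial by menopausal status, but neither shows that menopausal status predicts Ki67 change in normal lobules. At R² of 0.05 or less the gain is negligible or slightly negative. This stands too.

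Other points stand in part:

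- The 76% to 82% power belongs to the 8 mg/day analysis, which is not the primary one. The pooled primary comparison is at 80% to 85%. The step 3 simulation covers the pooled sample; only the perfect-balance figures in step 2 cover the subgroup.
- The simulated mixes are assumed. The increased-risk group was added in April 2023, after the first 12 women had been randomised, so the diagnosis mix cannot have been constant. The decimals should not be over-read.
- The 20-woman site yields about 20 × 0.4 × 0.86 ≈ 7 evaluable women per active arm. Main effects remain workable, but a rule for sparse levels is needed.
- The placebo contrast has 99.99% power unadjusted under the plan's assumptions (36 against 18, difference 50, SD 30), so adjustment there brings consistency rather than power.

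Finally, unadjusted is inferred from silence. Table 1 supports the inference, and if adjustment was intended the text still has to say so.

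**Conclusion.** The concern holds as a point of efficiency and pre-specification. The trial balances on three factors, and the described primary interval uses none of them. If they are prognostic, the interval is conservative and precision is given up. False non-inferiority is not inflated and the planned power is not lost.

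Under the stated simulation assumptions the trade is about 0.7 point of power lost if the factors explain nothing, against gains of about 2.6 points at R² = 0.1 and 8.9 at R² = 0.3. The direction is secure for any material R²; the size cannot be known from the documents.

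**What to change.** Before unblinding, state in section 11.0 that the gel–tamoxifen difference in percent change and its 95% interval come from a linear model with arm plus main effects for menopausal status, diagnosis (three levels) and site (three levels). Fit it to the primary analysis set already defined there: eligible women who started study drug and have Ki67 at both timepoints. Do not use the 2×3×3 = 18 cross-classified cells, which are too many for about 72 women. State a rule for pooling sparse levels. Keep the unadjusted interval as a sensitivity analysis, and use the same covariates for the placebo and volumetric density contrasts so that the estimates are consistent.

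No extra data or visits are needed, since the factors are recorded in RAVE before randomisation. The cost is five degrees of freedom and an amendment to section 11.0, which under section 8.0 needs IRB approval.

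### The non-inferiority rule in Section 11.0 is directionally wrong: read literally, it declares the gel non-inferior 97.5% of the time when its true deficit equals the 20-point margin

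*Combined protocol and SAP*

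**What the plan says.** The statistical analysis paragraph of Section 11.0 plans to assess non-inferiority by "estimating a 95% confidence interval for the mean" difference "in percent change between the two agents after four weeks of treatment". It then gives the decision rule: "if the lower limit of the confidence interval is less than the non-inferiority margin (described below), we will conclude that 4-OHT gel is non-inferior". The paragraph does not say which agent is subtracted from which, or whether the margin is positive or negative.

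The sample size/power paragraph of the same section supplies the margin, "with a non-inferiority margin of 20 percentage points", and illustrates it for a 50% reduction on tamoxifen: "4-OHT gel will be considered non-inferior if we can conclude that 4-OHT gel results in a mean reduction of Ki67 of at least 30" per cent. The planning assumptions are also there: "oral tamoxifen will lead to a 50% mean relative reduction in Ki67 in normal lobules at four weeks compared to baseline" and "We assume that the standard deviation for the percent change in Ki67 is 30 percentage points". The resulting claim is "A sample size of 36 per active treatment arm will provide >80% power at" alpha 0.05. Table 1 shows 80% power for 36 per group.

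**The concern.** A non-inferiority claim requires the interval to exclude a deficit as large as the margin. The limit that matters is the one on the side where the gel is worse, and it must fall on the acceptable side of the margin. The printed rule combines a lower limit with a less-than sign, and this does not work in either orientation.

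- **A. Positive means the gel is worse** (gel minus tamoxifen in percent change, margin +20). The upper limit must be below +20. A lower limit below +20 shows only that the data have not proved the gel worse than the margin.
- **B. Negative means the gel is worse** (gel minus tamoxifen in percent reduction, margin -20). The lower limit must be above -20. A lower limit below -20 means that a deficit beyond the margin has not been excluded, so the rule is met exactly when non-inferiority has not been shown.

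The sentence governs the primary hypothesis. Inferiority of the gel is also a real possibility in this trial. The Background reports that the gel at 4 mg/day was inferior to 20 mg oral tamoxifen on Ki67 in women with DCIS (between-arm p = 0.002), and Section 11.0 keeps the five gel participants treated at 4 mg/day in the main analysis.

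**Working it through.** **Inputs**, all from Section 11.0: 36 per active arm; SD of percent change 30 points; margin 20 points; two-sided 95% interval; tamoxifen reduction 50%. I assume normal data, equal variances and a t-based interval.

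**Step 1. Reproduce the stated power.**
- SE = 30 × √(2/36) = 7.07, with 36 + 36 − 2 = 70 degrees of freedom.
- Normal approximation, 2.5% in one tail: Φ(20/7.07 − 1.96) = Φ(0.87) = 80.7%. The noncentral t gives 79.7%.
- With 5% in one tail the power would be 88.2% (normal) or 87.6% (t), and 28 per arm would be enough.

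The plan's 36 per arm and 80% therefore correspond to a test in which a two-sided 95% interval excludes the margin. All eight powers in Table 1 reproduce within one point on the same basis.

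**Step 2. Error at the margin.** The critical value is t(0.975, 70) = 1.994, so the planned half-width is 1.994 × 7.07 = 14.1 points.
- Under A, with D = gel minus tamoxifen in percent change and a true D of +20: P(lower limit < 20) = P((estimate − 20)/SE < 1.994) = P(T < 1.994) = 97.5%.
- Under B, with a true difference of −20 in reduction, P(lower limit < −20) is the same probability, 97.5%.
- Neither result depends on the SD or the sample size.

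**Step 3. Other true deficits** (noncentral t, 70 df). The entries are the probability of declaring non-inferiority.

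| True gel deficit, points | As written, A: lower < +20 | As written, B: lower < −20 | Correct rule |
|---|---|---|---|
| 0 (gel equals tamoxifen) | about 100% | 20.3% | 79.7% |
| 10 | 99.96% | 71.4% | 28.6% |
| 20 (at the margin) | 97.5% | 97.5% | 2.5% |
| 30 | 71.4% | 99.96% | 0.04% |
| 50 (gel inactive) | 1.3% | about 100% | about 0 |

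Simulation with 100,000 trials per scenario, at deficits of 0, 20 and 50 points, agreed. At the margin it gave 97.5% as written (A and B) and 2.5% for the correct rule.

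**Step 4. In terms of observed results**, with the SE at its planned value. The correct rule needs an observed deficit below 20 − 14.1 = 5.9 points. Under A as written, any observed deficit below 20 + 14.1 = 34.1 points passes; with a 50% reduction on tamoxifen, a gel reduction of only about 16% (50 − 34.1) would be called non-inferior. Under B as written, the gel passes only if its observed deficit exceeds 5.9 points, the exact complement of the correct rule.

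**Step 5. A third literal reading.** Using the reduction scale with the margin as printed, a positive 20, the rule is met about 100% of the time at a 20-point deficit.

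**The case against.** The strongest defence is that the margin is given as an unsigned size. Suppose the difference is gel minus tamoxifen in reduction, and the sentence means that the lower limit must be smaller than 20 points in absolute size. The rule is then valid: simulation of that reading gives 2.5% at a 20-point deficit and about 80% at equality. The worked example points the same way and amounts to a second statement of the criterion. The power figures also match a correct test. On this view the trial is soundly designed and the sentence is loosely worded.

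Much of this stands. The intent can be recovered, and the sample size is not in question. Because the order of subtraction is missing, the documents do not show whether the wrong word is the limit (A) or the inequality (B). The practical result also depends on that choice: an inactive gel would pass 1.3% of the time under A but almost always under B.

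It does not rescue the sentence. The absolute-size reading is written nowhere, and the worked example names no confidence limit, sign or direction. A pre-specified rule should be applicable without inference once the treatment codes are known, and here the literal text conflicts with the evident intent.

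**Conclusion.** The concern holds. In both conventions where the signed margin represents a 20-point gel deficit, the rule as printed declares non-inferiority 97.5% of the time at the margin instead of 2.5%. This is conditional on the sentence being applied literally and rests only on the 95% level of the interval. The figures away from the margin also assume 36 per arm, an SD of 30 and a t-based analysis. No other part of the document corrects the rule, and the worked example and power calculation contradict it. It must be corrected because it decides the primary hypothesis.

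**What to change.** Replace the decision sentence in the statistical analysis paragraph of Section 11.0 with text such as:

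> Let D be the mean percent change in Ki67 on 4-OHT gel minus the mean percent change on oral tamoxifen, so that a positive D means less reduction with the gel. Non-inferiority is concluded if the upper limit of the two-sided 95% confidence interval for D is below +20 percentage points.

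On the reduction scale the equivalent is a lower limit above −20. State one form only, and say beside it that the test carries 2.5% in one tail, since the plan gives alpha as 0.05 without sidedness and its power figures assume 2.5%. Tie the worked example to the same D.

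The corrected rule has 2.5% error at the margin and 79.7% power at equality, in line with the planned 80%. The cost is a one-sentence amendment, with no effect on sample size, data collection or conduct. It should be in place before unblinding.
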